7.2 Participant Discontinuation/Withdrawal from the Study

- Parents/LARs will be informed that they have the right to withdraw their child from the study at any time.
- A participant may withdraw from the study at any time at his/her own request, or may be withdrawn at any time at the discretion of the Investigator for safety, behavioral, compliance, or administrative reasons. This is expected to be uncommon.
- The reason for withdrawal should be clearly documented in the source documents and in the CRB: Adverse Event, Lost to Follow-up, Protocol Deviation, or Withdrawal by Participant or Parent/LAR.
- If the participant withdraws consent for disclosure of future information, the Sponsor may retain and continue to use any data collected before such a withdrawal of consent.
- If a participant withdraws consent, he/she may request destruction of any samples taken and not tested, and the Investigator must document this in the site study records.
- Withdrawn participants will not be replaced.

Follow-up of Discontinuations

For participants who have prematurely terminated the study, the site should attempt to contact them and complete all scheduled safety follow-ups, except if they specified that they do not want to be contacted again and it is documented in the source document.

For participants where the reason for early termination is lost to follow-up, the site will not attempt to obtain further safety information. See [Section 7.3](#) for definition of “lost to follow-up”.

7.3 Lost to Follow-up

A participant will be considered lost to follow-up if he or she repeatedly fails to return for scheduled visits and is unable to be contacted by the study site.

The following actions must be taken if a participant fails to return to the site for a required study visit or cannot be contacted as planned in the SoA:

- The site must attempt to contact the participant and reschedule the missed visit as soon as possible and counsel the participant on the importance of maintaining the assigned visit schedule and ascertain whether or not the participant wishes to and/or should continue in the study.
- Before a participant is deemed lost to follow-up, the Investigator or designee must make every effort to regain contact with the participant (where possible, 3 telephone calls and, if necessary, a certified letter to the participant’s last known mailing address or local equivalent methods), or at least to determine his/her health status while fully respecting his/her rights. These contact attempts should be documented in the participant’s medical record.
- Should the participant continue to be unreachable, he/she will be considered to have withdrawn from the study.

Discontinuation of specific sites or of the study as a whole are handled as part of [Appendix 10.1](#).

8 Study Assessments and Procedures

- Study procedures and their timing are summarized in the SoA ([Section 1.3](#)). Protocol waivers or exemptions are not allowed.
- Immediate safety concerns should be discussed with the Sponsor immediately upon occurrence or awareness.
- Adherence to the study design requirements, including those specified in the SoA, is essential and required for study conduct.
- All screening evaluations must be completed and reviewed to confirm that potential participants meet all eligibility criteria. The Investigator will maintain a screening log to record details of all participants screened and to confirm eligibility or record reasons for screening failure, as applicable
- Exceptional situations (eg, COVID-19) may prevent access to the clinical trial sites. In these situations, site visits may be replaced by home visits where blood draw, physical examination and safety assessments will be performed by home nurses except for V1 (Group 1 and Group 2), V3 (Group 1), and V2 (Group 2), which will be conducted at the investigational site.

Blood samples will be collected as described in the SoA tables ([Section 1.3](#)). At V1 for all participants, 5 mL of blood will be collected in tubes provided by or recommended by the Sponsor. At V2, only participants in Group 1 who received study vaccination at V1 will provide a 5 mL blood sample. All participants are required to provide a blood sample at the Year 5 visit (V3 for Group 1, and V2 for Group 2) prior to receiving vaccination, and another blood sample 30 days post vaccination (V4 for Group 1 and V3 for Group 2).

Guidance and information for the sample collection, preparation, storage, and shipment are provided in the Operating Guidelines.

8.1 Efficacy and Immunogenicity Assessments

8.1.1 Efficacy Assessments

No clinical efficacy data will be obtained in the study.

8.1.2 Immunogenicity Assessments

Functional meningococcal antibody activity against serogroups A, C, Y, and W will be measured in a serum bactericidal assay utilizing the human complement (hSBA) and the baby rabbit complement (rSBA). The results will be expressed as vaccine seroresponse, seroprotection, and GMTs.

Antibodies to Meningococcal Antigens (hSBA Method)

Functional meningococcal antibody activity against serogroups A, C, Y, and W will be measured in a serum bactericidal assay utilizing human complement. Two-fold dilutions of test sera are prepared in sterile 96-well microtiter plates. Serogroup-specific meningococcal bacteria along with human complement are added to the serum dilutions and allowed to incubate. After this incubation period, an agar overlay medium is added to the serum/complement/bacteria mixture, allowed to harden, and then incubated overnight at 37°C with 5% carbon dioxide (CO₂). Bacterial colonies present in the wells are then counted. The endpoint titer is determined by the reciprocal serum dilution yielding $\geq 50\%$ killing as compared to the mean of the complement control wells. The lower limit of quantification (LLOQ) of the hSBA assay is a titer of 1:4.

The hSBA testing will be performed at [REDACTED]

Antibodies to Meningococcal Antigens (rSBA Method)

Functional meningococcal antibody activity against serogroups A, C, Y, and W will be measured in a SBA using a rabbit complement. Two-fold dilutions of test sera are prepared in sterile 96-well microtiter plates. Serogroup-specific meningococcal bacteria along with baby rabbit complement are added to the serum dilutions and allowed to incubate. After this incubation period, 10 μ L of the serum/complement/bacteria mixture is removed and added to a blood agar plate using the tilt method, and then incubated overnight at 37°C with 5% CO₂. Bacterial colonies present on the blood agar plate are then counted. The bactericidal titer of each sample is expressed as the final reciprocal dilution yielding $\geq 50\%$ killing as compared to the T60 (average number of bacteria in each control well after incubation) colony-forming unit (CFU). To report a titer greater than 1:4, clear bactericidal activity must be noted and the next dilution must have a CFU count less than the calculated 20% T60. The LLOQ of the rSBA assay is a titer of 1:4.

The rSBA testing will be performed at [REDACTED]

Antibody concentrations against tetanus toxoid contained in MenACYW conjugate vaccine as a carrier protein will be determined in children who received MenACYW conjugate vaccine approximately 5 or 10 years earlier as toddlers. The results will be expressed as percentage of participants with antibody concentrations to tetanus toxoid ≥ 0.01 international units (IU)/mL and ≥ 0.1 IU/mL, and geometric mean concentrations (GMCs).

Tetanus (diphtheria, tetanus, pertussis multiplexed electrochemiluminescent [DTP-ECL] assay)

Anti-tetanus antibodies will be measured by DTP-ECL assay, a multiplexed serological assay which allows for the simultaneous quantification of human antibodies to 6 specific antigens including diphtheria toxoid, tetanus toxoid, and 4 pertussis antigens: pertussis toxin, filamentous haemagglutinin, fimbriae and pertactin.

In this assay, each well of a 96-well microtiter plate is pre-coated in precise positions with the 6 different antigens in a multi-spot fashion. Following incubation with serum samples, antigen specific antibodies bind to the respective antigens. The captured antibodies are then detected using a sulfotag-conjugated anti-human immunoglobulin (Ig)G conjugate. Electrical stimulation of the conjugate in the presence of a chemiluminescent substrate results in the generation of a light signal from each specific spot that is captured by a camera in relative light units. The signal

generated is directly proportional to the amount of antibodies present in the sample, which is quantified using software and based on an established reference standard sample curve. For this study, only tetanus results will be calculated.

8.2 Safety Assessments

This section presents safety assessments other than AEs which are presented in [Section 8.3](#).

Planned time points for all safety assessments are provided in the SoA ([Section 1.3](#)).

8.2.1 Medical History

Prior to enrollment at V1 (Groups 1 and 2) and before administration of the booster vaccination at V2 (Group 2) / V3 (Group 1), participants will be assessed for pre-existing conditions and illnesses, both past and ongoing. Any such conditions will be documented in the source document. Significant (clinically relevant) medical history (reported as diagnosis) including conditions/illnesses for which the participant is or has been followed by a physician or conditions/illnesses that could resume during the course of the study or lead to an SAE or to a repetitive outpatient care will be collected in the CRB. The significant medical history section of the CRB contains a core list of body systems and disorders that could be used to prompt comprehensive reporting, as well as space for the reporting of specific conditions and illnesses.

For each condition, the data collected will be limited to:

- Diagnosis (this is preferable to reporting signs and symptoms)
- Presence or absence of the condition at enrollment

The reporting of signs and symptoms in lieu of a diagnosis is strongly discouraged.

Dates, medications, and body systems are not to be recorded, and the information collected will not be coded. Its purpose is to assist in the later interpretation of safety data collected during the study.

8.2.2 Physical Examinations

A physical examination as per standard of care (physical examination, including, but not limited to, general examination of the main body systems of interest [heart, lungs, skin, neurologic, muscular-skeletal, lymphatic system, etc]) will be performed at V1 for both groups, and at V2 (Group 2) / V3 (Group 1) by the Investigator or a delegate.

Information will be recorded in the source document.

If a routine examination had been performed within the last week by the Investigator, a sub-Investigator, or a licensed nurse practitioner, it does not need to be repeated unless there were some changes in health status, in which case it may be limited to the affected area.

8.2.3 Vital Signs

Oral, rectal, or axillary route (axillary preferred) pre-vaccination temperature using a certified standard digital thermometer will be systematically collected by the Investigator on the source document (including the route of measurement). Other types of thermometer (tympanic scan, temporal artery scan and infrared skin scan) are not allowed.

8.3 Adverse Events and Serious Adverse Events

The definitions of an AE, SAE, and the different categories of AEs can be found in [Appendix 10.2](#).

AEs will be reported by the participants/parents/LARs to the Investigator, then by the Investigator to the Sponsor.

The Investigator and any qualified designees are responsible for detecting, documenting, and recording events that meet the definition of an AE or SAE and remain responsible for following up AEs that are serious, considered related to the study intervention or study procedures, or that caused the participant to discontinue the study (see [Section 7](#)).

8.3.1 Time Period and Frequency for Collecting Adverse Event and Serious Adverse Event Information

Immediate Post-vaccination Observation Period

Participants will be kept under observation for 30 minutes after vaccination to ensure their safety. The post-vaccination observation should be documented in the source document.

Reactogenicity

Solicited injection site reactions will be collected from D01 to D08 after vaccination.

Solicited systemic reactions will be collected from D01 to D08 after vaccination.

The solicited injection site reactions and systemic reactions that are pre-listed in the DCs and CRB, together with the intensity scales, are presented in [Appendix 10.2.5.1.1](#).

Unsolicited Non-serious Adverse Events

Unsolicited non-serious AEs will be collected from D01 to D31 after vaccination.

The intensity grading scale for unsolicited non-serious AEs is presented in [Appendix 10.2.5.1.2](#).

Adverse Events of Special Interest

AESIs will be collected throughout the study.

See [Section 8.3.6](#) for the list of AESIs.

Serious Adverse Events

Information on SAEs will be collected and assessed throughout the study for both groups. However, for Group 2 before the first study intervention administration at V2, only SAEs related to study procedures (eg, blood sampling) are to be collected.

Medical occurrences that begin before the start of study intervention but after obtaining informed consent will not be recorded on the AE section of the CRB.

All SAEs will be recorded and reported to the Sponsor or designee immediately and under no circumstance should this exceed 24 hours, as indicated in [Appendix 10.2](#). The Investigator will submit any updated SAE data to the Sponsor within 24 hours of it being available.

Investigators are not obligated to actively seek AE or SAE after conclusion of the study participation. However, if the Investigator learns of any SAE, including a death, at any time after a participant has been discharged from the study, and he/she considers the event to be reasonably related to the study intervention or study participation, the Investigator must promptly notify the Sponsor.

8.3.2 Method of Detecting Adverse Events and Serious Adverse Events

Individual DCs, specifically designed for this study by the Sponsor and provided to the study sites, will be given to study participants' parents/LARs for the recording of daily safety information. These DCs will include pre-listed terms and intensity scales as well as areas for free text to capture additional safety information or other relevant details. Participants' parents/LARs will also be provided with rulers for measuring the size of injection site reactions, and with certified standard digital thermometers for measuring daily temperatures. To ensure consistency of reporting, the study sites will instruct participants' parents/LARs on how to correctly use these tools.

At specified intervals, the Investigator or an authorized designee will interview the participants' parents/LARs to collect the information recorded in the DC, and will attempt to clarify anything that is incomplete or unclear. All clinical study information gathered by the study site will be reported electronically by the Investigator or authorized designee using a web-based CRB. Any information that was not documented in the DC will first be captured in the source document and then reported electronically.

The method of recording, evaluating, and assessing causal relationship of AE and SAE and the procedures for completing and transmitting SAE reports are provided in [Appendix 10.2](#).

Care will be taken not to introduce bias when detecting AEs and/or SAEs. Open-ended and non-leading verbal questioning of the participants' parents/LARs is the preferred method to inquire about AE occurrences.

8.3.3 Follow-up of Adverse Events and Serious Adverse Events

Unless a participants' parents/LARs refuses further contact, each participant who experiences an AE (whether serious or non-serious) during the study must be followed until the condition resolves, becomes stable, or becomes chronic (even after the end of the participant's participation in the study) if *either* of the following is true:

- The AE is considered by the Investigator to be related to the study intervention administered.
- The AE caused the discontinuation of the participant from the study or from vaccination.

The Investigator will inform the Sponsor of the date of final disappearance of the event or the date of “chronicity” establishment.

8.3.4 Regulatory Reporting Requirements for Serious Adverse Events

- Prompt notification by the Investigator to the Sponsor of an SAE is essential so that legal obligations and ethical responsibilities towards the safety of participants and the safety of a study intervention under clinical investigation are met.
- The Sponsor has a legal responsibility to notify both the local regulatory authority and other regulatory agencies about the safety of a study intervention under clinical investigation. The Sponsor will comply with country-specific regulatory requirements relating to safety reporting to the regulatory authority, Institutional Review Board (IRB)/Independent Ethics Committee (IEC), and Investigators.
- For all studies except those investigating medical devices, Investigator safety reports must be prepared for suspected unexpected serious adverse reactions (SUSARs) according to local regulatory requirements and Sponsor policy and forwarded to Investigators as necessary.
- An Investigator who receives an Investigator safety report describing an SAE or other specific safety information (eg, summary or listing of SAEs) from the Sponsor will review and then file it and will notify the IRB/IEC, if appropriate according to local requirements.

8.3.5 Pregnancy

Pregnancy and/or the absence of the use of effective contraceptive methods, if required, will exclude vaccination at V3 (Group 1) / V2 (Group 2). However, a participant could potentially become pregnant during her participation.

Urine pregnancy testing will be performed, as applicable, before the V2 (Group 2) / V3 (Group 1) vaccination.

Details of all pregnancies in female participants will be collected after the start of study intervention and until delivery, and recorded in the Pregnancy CRF. Any data collected after CRF lock will be transmitted to the pharmacovigilance department on the paper form.

- If a pregnancy is reported, the investigator should promptly inform the Sponsor and will record pregnancy information together with the contraceptive method on the appropriate form and submit it to the Sponsor within 1 month of learning of the pregnancy.
- While pregnancy itself is not considered to be an AE or SAE, any pregnancy complication or elective termination of a pregnancy for medical reasons will be reported as an AE or SAE.
- Abnormal pregnancy outcomes (eg, spontaneous abortion, fetal death, stillbirth, congenital anomalies, ectopic pregnancy) are considered SAEs and will be reported as such.
- The participant will be followed to determine the outcome of the pregnancy. The investigator will collect follow-up information on the participant and the neonate and the information will be forwarded to the sponsor. Generally, follow-up will not be required for longer than [6 to 8 weeks] beyond the estimated delivery date, but will be in accordance with local regulations.

Any termination of pregnancy will be reported, regardless of fetal status (presence or absence of anomalies) or indication for the procedure.

- Any post-study pregnancy-related SAE considered reasonably related to the study intervention by the investigator will be reported to the sponsor as described in [Section 8.3.4](#). While the investigator is not obligated to actively seek this information in former study participants, he or she may learn of an SAE through spontaneous reporting.

Any female participant who becomes pregnant while participating in the study will discontinue study intervention until delivery or until delivery and end of lactation. However, the participant will be followed for safety assessment (and may be followed for immunogenicity assessment, if applicable).

8.3.6 Adverse Events of Special Interest

An AESI is an event for which ongoing monitoring and rapid communication by the Investigator to the Sponsor must be done. The following SAEs will be captured as serious AESIs throughout the study:

- Generalized seizures (febrile and non-febrile) (31)
- Kawasaki disease (32) (33) (34)
- GBS (35)
- Idiopathic thrombocytopenic purpura (ITP) (36)

These events have been listed as AESIs based on the feedback received from the EU regulators for the MenACYW conjugate vaccine.

No safety concerns relating to these AESIs have been identified with the use of MenACYW conjugate vaccine in the completed clinical trials.

Because of their medical importance and to ensure expedited communication to the Sponsor, these AESIs are to be considered as SAEs and reported to the Sponsor according to the procedure described in [Appendix 10.2.4](#). Further instructions on the data collection for these events and the relevant definitions will be provided in the CRB Completion Instructions.

8.4 Treatment of Overdose

Since the study intervention is administered by a health care professional, it is unlikely that overdose by injection occurs.

However, in the event of an overdose, the Investigator should:

- 1) Contact the Medical Monitor immediately
- 2) Closely monitor the participant for any AE/SAE
- 3) Document the quantity of the excess of the overdose in the source documents

8.5 Pharmacokinetics

Pharmacokinetics parameters are not evaluated in this study.

8.6 Pharmacodynamics

Pharmacodynamic parameters are not evaluated in this study.

8.7 Genetics

Genetics are not evaluated in this study.

8.8 Biomarkers

No other biomarkers than those described in the immunogenicity assessments section ([Section 8.1.2](#)) are evaluated in this study.

8.9 Immunogenicity Assessments

See [Section 8.1.2](#).

8.10 Medical Resource Utilization and Health Economics

Medical Resource Utilization and Health Economics parameters are not evaluated in this study.

9 Statistical Considerations

Clinical data will be analyzed under the responsibility of the Biostatistics Platform of the Sponsor. A statistical analysis plan (SAP) will be written and peer reviewed before any analyses. In accordance with the protocol, the SAP will describe all analyses to be performed by the Sponsor and all the conventions to be taken.

9.1 Statistical Hypotheses

Primary objective

Thirty days after the administration of MenACYW conjugate vaccine at V1, the sufficiency of the percentages of participants in Group 1 who achieve an hSBA vaccine seroresponse for meningococcal serogroups A, C, W, and Y will be tested.

Details on statistical methods are provided in [Section 9.4](#).

Secondary objectives

Immunogenicity: No hypotheses will be tested. The analyses will be descriptive.

Safety: The main parameters for the safety endpoints will be described by 95% CIs (based on the Clopper-Pearson method).

9.2 Sample Size Determination

All available and eligible participants, who participated in and completed the MET51 study (Groups 1 and 3) and received MenACYW conjugate vaccine as a part of the study, can be enrolled (approximately 500 participants), with approximately 250 participants each in MEQ00073 Group 1 and Group 2 (maximum estimate).

A sample size of 84 achieves at least 90.0% power to detect that the lower bound of the 1-sided 97.5% CI is greater than 0.75 (proportion under the null hypothesis) for the vaccine seroresponse to each serogroup using a 1-sided exact test with a significance level (alpha) of 0.025.

Table 9.1: Power of the study based on the primary objective

Antigen	Endpoint	Estimates* for MenACYW	Power (%)
A	Seroresponse	0.95	> 99.9
C	Seroresponse	0.90	92.6
Y	Seroresponse	0.95	> 99.9
W	Seroresponse	0.925	99.0
Global Power			> 90

*Estimated responses are based on the results of MET62 Group 1 that received 1 dose of MenACYW conjugate vaccine (estimates of MET62 minus 5%).

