Most participants in both study groups had a ≥ 4 -fold rise in rSBA antibody titers at D30. The percentages of participants with a ≥ 4 -fold rise in rSBA antibody titers 30 days after vaccination in Group 1 (92.3%, 94.9%, 100%, and 100%, respectively for serogroups A, C, W, and Y) were comparable to those in Group 2 (81.8%, 97.7%, 100%, and 100%, respectively for serogroups A, C, W, and Y).

rSBA Vaccine Seroresponse

Most participants in both study groups demonstrated an rSBA vaccine seroresponse at D30. The percentages of participants with an hSBA vaccine seroresponse were comparable in Group 1 (ranging from 92.3% to 100%) to those in Group 2 (ranging from 81.8% to 100%).

Overall, the MenACYW conjugate vaccine had comparable immune response in both study groups across all 4 serogroups.

This provides evidence that the MenACYW conjugate vaccine can boost MenACYW conjugate vaccine-primed children as well as Nimenrix vaccine-primed children.

In addition to the studies MET51 and MET62 described above, the relevant Phase III (MET35) study in children population (2 to 9 years of age) is discussed in the Investigator's Brochure (IB) Section 5.

Current Study MEQ00073

The MET51 study enrollment period was February 2017 to September 2017. There is now the opportunity to generate persistence and booster data approximately 5 and 10 years after vaccination with MenACYW conjugate vaccine in toddlers. Therefore, this MEQ00073 study will provide longer persistence data than in the MET62 study, with a larger sample size. It also is intended to further confirm that the MenACYW conjugate vaccine can boost MenACYW conjugate vaccine-primed children and adolescents. The boostability of MenACYW conjugate vaccine in children who were MenACYW conjugate vaccine-primed as toddlers will be determined by sufficiency of the seroresponse measured using hSBA 30 days post-booster in

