1.2. Sample Size Determination

All available and eligible participants, who participated in and completed the MET51 study (Groups 1 and 3) and received MenACYW conjugate vaccine as a part of the study, can be enrolled (approximately 500 participants), with approximately 250 participants each in MEQ00073 Group 1 and Group 2 (maximum estimate).

A sample size of 84 achieves at least 90.0% power to detect that the lower bound of the 1-sided 97.5% CI is greater than 0.75 (proportion under the null hypothesis) for the vaccine seroresponse to each serogroup using a 1-sided exact test with a significance level (alpha) of 0.025.

Table 3.1: Power of the study based on the primary objective

Antigen	Endpoint	Estimates* for MenACYW	Power (%)
A	Seroresponse	0.95	> 99.9
C	Seroresponse	0.90	92.6
Y	Seroresponse	0.95	> 99.9
W	Seroresponse	0.925	99.0
Global Power			> 90

*Estimated responses are based on the results of MET62 Group 1 that received 1 dose of MenACYW conjugate vaccine (estimates of MET62 minus 5%).

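### Do the response rates behind the Table 9.1 power figures contradict the MET62 results printed in the protocol?

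*Protocol*

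**What the plan says.** Protocol section 9.2 sizes the primary objective, hSBA seroresponse in Group 1, against a fixed threshold: "A sample size of 84 achieves at least 90.0% power to detect that the lower bound" of the interval exceeds 75%, "using a 1-sided exact test with a significance level (alpha) of 0.025". Table 9.1 assumes 0.95 for A, 0.90 for C, 0.95 for Y and 0.925 for W. It reports power of >99.9%, 92.6%, >99.9% and 99.0%, with global power above 90%. The footnote traces the assumptions to MET62: "Estimated responses are based on the results of MET62 Group 1 that received 1 dose of MenACYW conjugate vaccine (estimates of MET62 minus 5" per cent). SAP section 1.2 repeats the table as Table 3.1, with the same footnote ("estimates of MET62 minus 5" per cent).

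The MET62 results are summarised in Protocol section 2.1. The 4-fold rises in rSBA titer are listed "in Group 1 (92.3%, 94.9%, 100%, and 100%, respectively for serogroups A, C, W, and Y"). The next paragraph is headed as rSBA seroresponse and opens with a sentence about rSBA. Its second sentence then reads: "The percentages of participants with an hSBA vaccine seroresponse were comparable in Group 1 (ranging from 92.3% to 100" per cent), with a Group 2 range of 81.8% to 100%.

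Section 9.2 also expects about 250 participants in Group 1, described as a maximum estimate.

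**The concern.** The footnote invites the reader to take the MET62 results, subtract 5 and arrive at Table 9.1. With the percentages printed in section 2.1 this fails for two of the four serogroups: A is 7.7 points higher in the table and W is 2.5 points lower.

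Taken at face value, the sentence labelled hSBA is worse. If the lowest MET62 hSBA seroresponse was 92.3%, some serogroup should enter the table at 0.873, yet the lowest entry is 0.90. No allocation of the range to serogroups avoids that.

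At stake would be the claim that 84 participants suffice. At 0.873 they would not give 90% power for that serogroup, or for all four together.

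**Working it through.** **1. Reproducing Table 9.1.** Inputs from section 9.2: n = 84, null proportion 0.75, one-sided alpha 0.025. The critical count is the smallest r whose Clopper-Pearson lower limit exceeds 0.75.

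- r = 71: lower limit 0.7499; P(X ≥ 71 | 84, 0.75) = 0.0251, just too large.
- r = 72: lower limit 0.7638; P(X ≥ 72 | 84, 0.75) = 0.0126. So 72 of 84 are needed.

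Power(p) = Σ over k = 72 to 84 of C(84, k) p^k (1 − p)^(84 − k).

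- p = 0.95: 99.97%
- p = 0.925: 99.03%
- p = 0.90: 92.59%

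Global power, taking the serogroups as independent: 0.9997² × 0.9259 × 0.9903 = 91.6%. The Bonferroni lower bound, which needs no independence, is also 91.6%. Every entry in the table is confirmed.

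**2. Inputs against the printed MET62 figures** (5% read as points).

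| Serogroup | Table 9.1 | Implied MET62 value (+5) | Printed rSBA 4-fold rise | Printed value − 5 |
|---|---|---|---|---|
| A | 0.95 | 100% | 92.3% | 0.873 |
| C | 0.90 | 95% | 94.9% | 0.899 |
| Y | 0.95 | 100% | 100% | 0.95 |
| W | 0.925 | 97.5% | 100% | 0.95 |

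**3. What 0.873 would mean at n = 84.** Power is 73.4%. If 5% is relative, p = 0.923 × 0.95 = 0.877 and power is 77.0%. Global power is 67.6% with all four values in the last column, and 67.3% if only A changes. It cannot exceed the 73.4% of the weakest serogroup.

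**4. Which assay does 92.3% belong to?**

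- The MET62 results in section 2.1 are introduced as measured by rSBA. The paragraph has an rSBA heading and an rSBA opening sentence.
- The Group 1 range (92.3% to 100%) and the Group 2 range (81.8% to 100%) both coincide with the rSBA 4-fold-rise ranges just above.
- That coincidence is what rSBA data must give, if MET62 used the rSBA seroresponse definition in section 9.4.3.1. For a pre-vaccination titer of at least 1:8, seroresponse is a 4-fold rise. For a titer below 1:8, it needs at least 1:32 afterwards. Section 2.1 says every participant in both MET62 groups reached at least 1:128 at Day 30. Anyone starting below 1:8 therefore met the 1:32 rule and also rose more than 128/8 = 16-fold. The two rSBA percentages are then identical serogroup by serogroup.

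The range is thus the rSBA seroresponse range, and the word hSBA is very probably a slip. Table 9.1 supports an hSBA endpoint with a different rule for low starters (at least 1:16), so the comparison in step 2 crosses assays.

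**5. Are the implied hSBA values possible?** MET62 Group 1 enrolled 42. As an illustration, 38/40 = 95.0% and 39/40 = 97.5%; or 37/39 = 94.9% and 38/39 = 97.4%, which minus 5 points round to 0.90 and about 0.925. The documents neither confirm nor refute these counts, but nothing rules the values out.

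**6. Power at other sizes if 0.873 were nevertheless right.**

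| Evaluable n | Serogroup at 0.873 | All four (0.873, 0.899, 0.95, 0.95) |
|---|---|---|
| 84 | 73.4% | 67.6% |
| 100 | 87.1% | 85.2% |
| 120 | 92.1% | 91.3% |
| 150 | 96.1% | 95.9% |
| 200 | 99.3% | 99.3% |
| 250 | 99.9% | 99.9% |

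Power stays at or above 90% from n = 118 for the single serogroup and from n = 123 for all four.

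**The case for a change.** The strongest reply is that the reader loses either way. If the sentence labelled hSBA is right, the claim for 84 fails. If it is wrong, neither document shows a MET62 hSBA seroresponse to support the power calculation for the primary endpoint. Section 4.2 says the MET62 results are in the Investigator's Brochure and in the protocol, so one might expect to trace them here. The 250 is only a maximum, and re-enrolment after five years, the split into two groups and per-protocol exclusions could leave fewer.

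Part of this stands: the inputs cannot be traced from these documents, and the footnote does not say whether 5% is absolute or relative. But an unprinted source is not a contradicted one, and section 4.2 names the Brochure as a place where the results are held. The evidence for the first branch is one word that its own heading, the sentence before it and the figures all contradict. A real shortfall would need two things together: that the word is right after all, and that fewer than about 118 to 123 participants are evaluable.

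Nor can serogroup A be singled out as weakest from MET51. The 68.8% seroprotection in MenC-CRM-primed toddlers is matched by 68.1% for W, and W is below A on every MenACYW measure in Table 2.1. Those are also responses to a first dose, not to a booster.

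**Conclusion.** The concern does not hold as a fault in the power calculation. Table 9.1 and SAP Table 3.1 are right for their stated inputs (91.6% globally at n = 84), and the documents do not show those inputs to be wrong. The apparent contradiction comes from reading an rSBA figure as hSBA.

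What is left is a clerical slip in section 2.1 and source values that are not printed. Neither affects the conduct of the trial or its result: the primary test compares the observed lower confidence limit with 75% and uses none of the assumed rates. Printing the source values would help a reader but would alter no analysis or conclusion.

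This rests on two assumptions: that 92.3% is an rSBA result, which section 2.1 supports strongly but cannot prove, and that evaluable enrolment in Group 1 is well above 84. If the first failed, power at 84 would be about 73% for one serogroup and 67% to 73% overall, but 99.9% at 250.
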